7.8.11. Safety Analysis

All safety analyses will be performed using the Safety Population.

7.8.11.1. Adverse Events

Adverse event verbatim terms will be coded in the EDC system against Medical Dictionary for Regulatory Activities (MedDRA) version 22.0.

During the TE Period, an AE that has a start date during the TE Period (from the date of the first dose to 1 day after the last dose of double-blind study drug) will be considered a TEAE. For the TE Period, the number and percentage of patients reporting TEAEs in each treatment group will be tabulated:

- By system organ class (SOC) and preferred term (PT)
- By SOC, PT, and severity
- By SOC, PT, and relationship to study drug

If a patient has more than one TEAE coded to the same PT or SOC, the patient will be counted only once for that PT or SOC by identifying those TEAEs with the highest severity and the closest relationship to study drug.

The incidence of the following TEAEs will be summarized by PT:

- Common ($\geq 2\%$ of patients in any treatment group) TEAEs
- Treatment-emergent SAEs
- TEAEs leading to premature discontinuation of study drug

In addition, the incidence of SAEs, fatal SAEs (ie, events with an outcome of death), if any, will be summarized separately by treatment group and PT within the period from the first dose to 30 days after the last dose of study drug.

AE Listings will be presented for all patients with AEs, screened patients with SAEs, patients with AEs leading to discontinuation, and patients who died (if any), respectively.

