8.2.1.2 Classification of an Adverse Event

8.2.1.2.1 Severity

The investigator or delegated physician will provide an assessment of the severity of each AE by recording a severity rating in the patient's source documentation and on the AE page of the patient's eCRF. *Severity*, which is a description of the intensity of manifestation of the AE, is distinct from *seriousness*, which implies a patient outcome or AE-required treatment measure associated with a threat to life or functionality. Severity will be assessed according to the following scale:

Mild: A type of AE that is usually transient and may require only minimal treatment or therapeutic intervention. The event does not generally interfere with usual activities of daily living.

Moderate: A type of AE that is usually alleviated with additional specific therapeutic intervention. The event interferes with usual activities of daily living, causing discomfort, but poses no significant or permanent risk of harm to the research participant.

Severe: A type of AE that interrupts usual activities of daily living, or significantly affects clinical status, or may require intensive therapeutic intervention.

AEs should be recorded using the maximum intensity of the event (eg, if a patient reported nausea lasting 3 days, 1 start date and 1 stop date should be recorded along with the maximum intensity experienced for that event over that 3-day timeframe).

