10.6.1 Adverse Events

Adverse Event Verbatim Terms will be coded in the EDC system against the most current version of the Medical Dictionary for Regulatory Activities (MedDRA) available at the start of the study (or newer).

An AE that occurs during the Treatment Period (up to 1 day after the last dose of double-blind study drug) will be considered a TEAE for the Treatment Period if it was not present prior to the date of the first dose of double-blind study drug, or was present prior to the date of the first dose but increased in severity during the Treatment Period.

If more than one AE is reported prior to the first dose of double-blind study drug and coded to the same preferred term, the AE with the greatest severity will be used as the benchmark for comparison with the AEs occurring during the Treatment Period that were also coded to that preferred term. An AE that occurs more than 1 day after the last dose of double-blind study drug will not be counted as a TEAE.

For the Treatment Period, the number and percentage of patients reporting TEAEs in each treatment group will be tabulated by system organ class (SOC) and preferred term; by SOC, preferred term, and severity; and by SOC, preferred term, and relationship to study drug. If a patient has more than one TEAE coded to the same preferred term, the patient will be counted only once for that preferred term by identifying those TEAEs with the highest severity and the closest relationship to study drug.

The distribution of TEAEs by severity and relationship to study drug will be summarized by treatment group for the Treatment Period.

The incidence of common TEAEs, on-therapy SAEs, and AEs leading to premature discontinuation of study drug will be summarized by preferred term and treatment group for the Treatment Period. In addition, the incidence of fatal SAEs (ie, events with an outcome of death), if any, will be summarized separately by treatment group and preferred term for the Treatment Period.

Listings will be presented for patients with SAEs, patients with AEs leading to discontinuation, and patients who died (if any).

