5.6.1. Adverse Events

Adverse Event

An AE is any untoward medical occurrence associated with the use of a drug in humans, whether or not considered drug-related.

An AE, therefore, can be any unfavorable and unintended sign (including an abnormal laboratory finding, for example), symptom, or disease temporally associated with the use of a medicinal product, whether or not considered related to the medicinal product.

Note: A procedure is not an AE, but the reason for a procedure may be an AE.

Treatment-emergent Adverse Event

A TEAE is an event that emerges, or a preexisting event that worsens (with a new start date), any time after administration of the first dose of study drug (Day 1) during the treatment emergent period, which is defined as the date of the first treatment to the date on or before 1 day after the date of the last treatment. The Investigator will provide an assessment of the AE relationship to study drug and AE severity for each AE.

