5.6.1.2. Classification of Adverse Event Severity

The investigator or delegated physician will provide an assessment of the severity of each AE by recording a severity rating in the patient’s source documentation and on the AE page of the patient’s eCRF. *Severity*, which is a description of the intensity of manifestation of the AE, is distinct from *seriousness*, which implies a patient outcome or AE-required treatment measure associated with a threat to life or functionality. Severity will be assessed according to the following scale:

- **Mild:** A type of AE that is usually transient and may require only minimal treatment or therapeutic intervention. The event does not generally interfere with usual activities of daily living.

- **Moderate:** A type of AE that is usually alleviated with additional specific therapeutic intervention. The event interferes with usual activities of daily living, causing discomfort, but poses no significant or permanent risk of harm to the research participant.
- **Severe:** A type of AE that interrupts usual activities of daily living, or significantly affects clinical status, or may require intensive therapeutic intervention.

AEs should be recorded using the maximum intensity of the event (eg, if a patient reported nausea lasting 3 days, 1 start date and 1 stop date should be recorded along with the maximum intensity experienced for that event over that 3-day timeframe).

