7.8.1.1. Analysis Periods

For the purpose of analyses, three analysis periods are defined and will be used for different analyses.

The Pretreatment period is defined as the 14 days immediately prior to the date of the first dose of study drug.

The Treatment Period is defined as the period from the date of the first dose of study drug to the date of the last dose of study drug. This will be used as the primary efficacy analysis period unless otherwise specified.

The Treatment Emergent Period (TE Period) is defined as the period from the date of the first dose of study drug to 1 day after the date of the last dose. For analysis purposes, AEs and required medications will be considered treatment emergent if they occur within this period. TE period will be the primary analysis period for AEs and medications.

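### The SAP's start-date rule for TEAEs conflicts with how AEs are recorded, so an AE opened before first dose that worsens on drug can be left out of the TEAE tables

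*SAP*

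**What the plan says.** Four places bear on this point.

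- **Counting rule, SAP 7.8.11.1.** A TEAE is "an AE that has a start date during the TE Period (from the date of the first dose to 1 day after the last dose". Neither a severity increase nor a comparison with pre-dose severity appears.
- **Counting rule, Protocol 10.6.1.** An AE also counts if it "was present prior to the date of the first dose but increased in severity during the Treatment Period". Where several pre-dose AEs share a preferred term, "the AE with the greatest severity will be used as the benchmark for comparison with the AEs occurring during the Treatment Period" carrying the same term.
- **Definition, SAP 5.6.1.** A TEAE includes "a preexisting event that worsens (with a new start date), any time after administration of the first dose of study drug (Day 1"). SAP 7.8.1.1 adds that "AEs and required medications will be considered treatment emergent if they occur within this period".
- **Recording rule, Protocol 8.2.1.2.1 and SAP 5.6.1.2.** "AEs should be recorded using the maximum intensity of the event". The example given is nausea lasting three days, for which "1 start date and 1 stop date should be recorded along with the maximum intensity experienced for that event".

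SAP Appendix 1, which lists changes from the protocol analyses, presents the split between Treatment Period and Treatment Emergent Period as a clarification. It does not mention the severity clause or the benchmark.

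**The concern.** The definition in SAP 5.6.1 and the count in SAP 7.8.11.1 agree only if a worsened event carries a second start date. Nothing in either document tells sites to close an AE that was open before dosing and start a new record when it worsens afterwards. A site that follows the recording rule literally keeps one record, with the pre-dose start date and the highest grade reached. The SAP's counting rule then passes over that record, although both the protocol and the SAP's own definition call the event treatment-emergent.

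Safety and tolerability come first among the stated objectives, and Protocol 3.3 says this is the first study of linaclotide in IBS-D. Up to 49 days can pass between consent and first dose, including medication washout. Protocol 8.2.1.3 puts pre-dose AEs of randomized patients on the eCRF, so such records will exist. If drug makes some of these events worse, the missed ones would fall mainly in the active arms.

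The discontinuation table is exposed in the same way. Protocol 10.6.1 summarizes AEs that lead to stopping study drug, whereas SAP 7.8.11.1 restricts that table to TEAEs.

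**Working it through.** The plan gives no figure for this point, so there is none to reproduce. The check applies the two counting rules to five constructed AE histories. Day 1 is the first dose and Day 84 the last, so the TE Period runs from Day 1 to Day 85.

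| History | SAP 7.8.11.1 | Protocol 10.6.1 |
|---|---|---|
| A. AE starts Day -5, worsens on Day 10, kept as one record at its maximum grade | not counted | counted |
| B. Same event, with a new record and start date on Day 10 | counted | counted |
| C. Condition present at screening, AE first opened when it deteriorates on Day 10 | counted | counted |
| D. AE before dosing resolves, recurs on Day 10 at the same grade | counted | not counted |
| E. New AE starting on Day 1 after dosing | counted | counted |

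Three things follow.

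1. The loss arises only in history A. It depends on how sites record the event, and the written recording rule points to A rather than B.
2. The rules also differ in the other direction. In history D the SAP counts a recurrence at unchanged severity that the protocol benchmark excludes. Appendix 1 does not list this difference either.
3. Restoring the protocol clause would not by itself rescue history A. One record with one maximum grade does not show whether the peak came before or after dosing. If that grade were read as the pre-dose grade, the benchmark itself would be too high.

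**Scale.** With 92 patients per arm, 1/92 = 1.09% and 2/92 = 2.17%. SAP 7.8.11.1 tabulates as common the TEAEs that reach at least 2% in any arm. Where two patients in an arm have a term, missing one takes that arm from above the cut-off to below it.

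**Total.** The documents give neither the share of patients with an AE ongoing at first dose nor the share of those AEs that worsen. As an illustration only, assume 5% to 10% for the first and 10% to 20% for the second, with every such AE kept as one record. Then 368 × 0.05 × 0.10 = 1.8 and 368 × 0.10 × 0.20 = 7.4 events over four arms, or about 0.5 to 1.8 per arm across all preferred terms. These rates have no source in the documents, and the conclusion does not rest on them.

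**The case against.** The strongest reply is that the SAP does handle worsening. Section 5.6.1 defines it as treatment-emergent and attaches a new start date, and 7.8.11.1 merely puts that definition into operation. The protocol benchmark likewise compares pre-dose AEs with on-treatment AEs of the same term, which presupposes separate records. The maximum-intensity rule sits in the severity-grading section, and its example does not cross first dose. The eCRF completion instructions are not among the documents and may already require a new record.

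Other recording rules also narrow the gap. Protocol 8.2.1.3 has a condition present at screening recorded as an AE if it deteriorates, and asks for onset and duration of each episode of an intermittent AE. Protocol 8.2.1.2.3 treats worsening of abnormal values or conditions under treatment at baseline in a similar way. Most IBS symptoms were present at screening and so fall under history C. Events missing from the tables would still appear in the AE listings, and bowel function is analyzed separately from the eDiary.

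Much of this stands. A reader might infer that worsened pre-dose AEs are certain to be lost, or that the SAP makes no provision for worsening. The documents support neither reading. What remains is that the assumed new start date is not backed by any instruction in the two documents. The screening-condition rule does not cover an AE opened after consent and before dosing that then worsens further. Listings do not replace the between-arm tables.

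**Conclusion.** The point holds as a conflict between stated rules. SAP 7.8.11.1 counts by start date alone. It omits the severity clause and preferred-term benchmark of Protocol 10.6.1 without listing the omission in Appendix 1, and it relies on a start date that the recording rule does not generate. An AE opened between consent and first dose that worsens on drug can therefore be absent from the TEAE tables, including the one for discontinuations. A condition present at screening whose deterioration is first recorded as an AE on drug is not affected.

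The size is unknown. It depends on how many AEs are open at first dose, how many then worsen, and how sites record them. A reader might infer that TEAE rates are biased downward overall. That does not follow, because the SAP rule also admits recurrences at unchanged severity, and the net direction cannot be derived. The arm size fixes only the resolution: one patient is 1.09 percentage points. This is worth correcting before unblinding because the correction is specific and cheap.

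**What to change.** Reconcile the passages in three steps.

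1. **Recording.** State in the AE recording rule that when an AE already open before first dose becomes more severe after dosing, the increase is entered as a new record with its own start date and severity. The earlier record keeps its pre-dose maximum. Query every AE ongoing at Day 1, so that records already entered are covered as well.
2. **Counting.** Restore in SAP 7.8.11.1 the severity-increase clause of Protocol 10.6.1 and its benchmark of the greatest pre-dose severity for the preferred term. Step 1 must accompany this, because the clause cannot be applied to a single maximum-grade record.
3. **Disclosure.** List in SAP Appendix 1 any departure from Protocol 10.6.1 that is kept, including the treatment of same-severity recurrences and the restriction of the discontinuation table to TEAEs.

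The cost is SAP wording, a line in the eCRF completion instructions, one data query and minor programming. No extra patients or visits are needed.

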In a previously conducted Phase 2b trial utilizing MD-7246 (formerly known as linaclotide DR2), MCP-103-204, the standard deviation for the change from baseline to Week 12 in abdominal pain at its worst ranged from 2.32 to 2.88. Assuming a clinically meaningful treatment difference between MD-7246 and placebo of 1.0 for the mean change from baseline to Week 12 in abdominal pain, a standard deviation of 2.4, and 92 patients per treatment group (368 total), the estimated power is approximately 80% to detect a difference between each MD-7246 dose and placebo at a 2-sided significance level of 0.05 using a 2-sample t-test.

Final Date: 29 January 2019

SCHEDULE OF EVALUATIONS

Schedule of Evaluations MCP-103-205								
Study Period →	Screening Period (Up to 28 days)	Pretreatment Period (14 to 21 days)	Treatment Period (12 weeks)					Posttreatment Period (2 weeks)
Visit Days →	Screening Visit (Day -49 to Day -15)	Pretreatment Visit (Day -21 to Day -14)	Randomization Visit (Day 1)	Week 2 Phone Call (Day 15±3)	Week 4 Visit (Day 29±3)	Week 8 Visit (Day 57±3)	Week 12/ End-of-Treatment Visit ^p (Day 85+3)	End-of-Study Follow-up Phone Call (Day 99+3)
Visit Numbers →	Visit 1	Visit 2	Visit 3	Telephone Call	Visit 4	Visit 5	Visit 6	Telephone Call
Study Procedure ↓								
Signature of ICF	X							
Inclusion and Exclusion Criteria Verification	X	X	X*					
IWRS Registration ^a	X	X	X [†]		X	X	X	
Medical History	X							
Physical Examination ^b	X						X	
Body Weight and Height ^c	X	X	X*		X	X	X	
Seated Vital Signs ^d	X	X	X*		X	X	X	
Prior and Concomitant Medicines ^e	X	X	X*	X	X	X	X	X
Clinical Laboratory Tests ^f	X		X*		X	X	X	
Pregnancy Test ^g	X		X*				X	
Prohibited Medications Washout Instructions	X							
Loperamide for Diarrhea Dispensed ^h	X	X	X		X	X	X	
AE Evaluations ⁱ		X	X*	X	X	X	X	X
eDiary Registration and Training ^j		X	X*		X	X	X	
Pain Catastrophizing Scale		X						
Daily and Weekly Assessments ^k				X				
Patient eDiary Entry, in Clinic		X	X*		X	X	X	

Schedule of Evaluations MCP-103-205								
Study Period →	Screening Period (Up to 28 days)	Pretreatment Period (14 to 21 days)	Treatment Period (12 weeks)					Posttreatment Period (2 weeks)
Visit Days →	Screening Visit (Day -49 to Day -15)	Pretreatment Visit (Day -21 to Day -14)	Randomization Visit (Day 1)	Week 2 Phone Call (Day 15±3)	Week 4 Visit (Day 29±3)	Week 8 Visit (Day 57±3)	Week 12/ End-of-Treatment Visit ^P (Day 85+3)	End-of-Study Follow-up Phone Call (Day 99+3)

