5.1.1.4 Posttreatment Period

The Posttreatment Period starts on the day following the last day of dosing (Week 12/EOT Visit) and finishes 2 weeks later at the End of Study (EOS) Follow-up Phone Call. During the call, patients will be asked to report any AEs and medicines taken since the Week 12/EOT Visit and detail any other symptoms or comments they may have (at the discretion of the investigator, patients may be requested to return to the study center for their EOS Follow-up).

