5.3 STUDY DURATION

The test product and reference therapy will be administered for 12 weeks. Total patient participation will be up to 151 days, including the Screening, Pretreatment, Treatment, and Posttreatment Periods.

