8.2.1.3 Procedures for Recording Adverse Events

The investigator will record all AEs from the time informed consent is obtained until completion of study participation (eg, early termination or EOS Follow-up Phone Call). At each study visit, the investigator will inquire about the occurrence of AEs/SAEs since the last visit.

The occurrence of an AE or SAE may come to the attention of study center personnel during study visits and interviews of a study patient presenting for medical care, or upon review by a site monitor. All AEs including SAEs will be captured on the appropriate eCRF. Information to be collected includes event description, time of onset, clinician's assessment of severity, relationship to study drug (assessed only by those with the training and authority to make a diagnosis), and time of resolution/stabilization of the event. All AEs occurring while on study must be documented appropriately regardless of relationship. All SAEs will be followed to adequate resolution or stabilization for up to a maximum of 30 days after last dose.

Any medical condition that is present at the time that the patient is screened and does not deteriorate (worsen in severity and/or frequency) should be recorded as Medical History and not as an AE. However, if the patient's condition deteriorates at any time during the study, it will be recorded as an AE. AEs characterized as intermittent require documentation of onset and duration of each episode.

Pretreatment AEs will be collected and captured in the patient's source documentation from the time the patient signs the ICF until the patient receives study drug. Pretreatment AEs in randomized patients will additionally be entered on the AE page of the patient's eCRF.

Laboratory abnormalities, changes in vital signs, and physical examination findings should be considered AEs and reported on the AE page of the patient's eCRF only if the investigator considers them clinically significant and/or they necessitate intervention.

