3.2. Discussion of Study Design, Including Choice of Control Group

A double-blind, placebo-controlled, parallel-group study design was chosen in accordance with the concepts in ICH E10, Choice of Control Groups and Related Issues in Clinical Trials, in order to provide comparable treatment groups and minimal chance of selection or investigator bias. The study has a 14-21 day Pretreatment Period to establish patient baseline values without study drug and to familiarize patients with data collection methodology (ie, eDiary), a 12-week Treatment Period to compare the test treatment to a placebo control, and a 2-week Posttreatment Period to assess safety after MD-7246 treatment has been withdrawn.

The study will evaluate the effect of the test treatment on abdominal pain in IBS-D patients. Because the test treatment is not expected to significantly affect bowel function, loperamide will be provided beginning at the Screening Visit for patients to use as needed, at the patients' discretion, to stabilize their diarrhea throughout the study; utilization of loperamide for diarrhea will be recorded on an event-driven basis.

Three doses of MD-7246 were selected to assess the relationship between dose and response.

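### The 30-day SAE summary runs past the period in which new SAEs are collected, and non-serious AEs from the Posttreatment Period are listed but not tabulated by arm

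*SAP*

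**What the plan says.** Besides a table of treatment-emergent SAEs, SAP 7.8.11.1 plans a by-arm summary of SAEs and fatal SAEs "within the period from the first dose to 30 days after the last dose of study drug".

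On collection, Protocol 8.2.1.3 has the investigator record all AEs from consent "until completion of study participation (eg, early termination or EOS Follow-up Phone Call". Protocol 5.1.1.4 says the Posttreatment Period "finishes 2 weeks later at the End of Study (EOS) Follow-up Phone Call", and the Schedule of Evaluations places the "End-of-Study Follow-up Phone Call (Day 99+3" days. A 30-day limit does appear in Protocol 8.2.1.3, for a different task: "All SAEs will be followed to adequate resolution or stabilization for up to a maximum of 30 days after last dose". Protocol 8.2.1.4 repeats that follow-up limit. It also refers to an SAE reporting period without giving its length.

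For other AEs, Protocol 10.6.1 states: "An AE that occurs more than 1 day after the last dose of double-blind study drug will not be counted as a TEAE". SAP 7.8.1.1 adopts the same limit in its Treatment Emergent Period, and the remaining AE tables in SAP 7.8.11.1 are tied to it. AEs that start later are reached by the listing of all patients with AEs. Yet SAP 3.2, like Protocol 5.2, describes a "2-week Posttreatment Period to assess safety after MD-7246 treatment has been withdrawn".

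**The concern.** Two plans do not meet. The supplementary SAE and death summary names a window about twice as long as the period in which sites are told to record new events. A reader of the study report would take a 30-day window as 30 days of ascertainment. An empty row could then mean that no event occurred or that nobody asked.

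The second mismatch runs the other way. Non-serious AEs are collected for about two weeks after dosing, for a stated purpose, and no table summarizes them by arm. No laboratory tests or vital signs are scheduled at the End-of-Study call, so AEs are the main safety data from that period. Safety and tolerability are named first among the objectives, and Protocol 3.3 says this is the first study of linaclotide in IBS-D.

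**Working it through.** **1. Reproduce the timeline.** The Schedule of Evaluations runs from Day -49 at the earliest to Day 99+3 = Day 102 at the latest, with no Day 0. That is 49 + 102 = 151 days, which agrees with Protocol 5.3: "Total patient participation will be up to 151 days". The last planned contact is therefore Day 102 at the latest.

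**2. Days of AE recording after last dose.** Last dose is taken at the Week 12 visit (Day 85+3) and the call is on Day 99+3.
- Nominal: 99 − 85 = 14 days.
- Shortest: 99 − 88 = 11 days.
- Longest: 102 − 85 = 17 days.

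**3. Part of the 30-day window without planned recording.**
- Nominal: 30 − 14 = 16 days (53%).
- Range: 30 − 17 = 13 days (43%) to 30 − 11 = 19 days (63%).

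The window closes on Day 85 + 30 = 115 to Day 88 + 30 = 118, after the last planned contact.

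**4. Which 30-day rule is which.** Protocol 8.2.1.3 and 8.2.1.4 set 30 days as the maximum for following an SAE to resolution or stabilization. Neither tells sites to look for new SAEs after the End-of-Study call. SAP 7.8.11.1 does not say whether its window applies to SAE onset or to date of death. Protocol 10.6.1 summarizes on-therapy SAEs and fatal SAEs for the Treatment Period. SAP Appendix 1, which lists changes from the protocol, does not mention the 30-day window.

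**5. Expected new SAEs in the uncovered days.** Formula: 368 × (12-week SAE rate) × 16/84. Protocol 3.3 reports 2 patients with 3 on-therapy SAEs in the 12-week Phase 2b trial. The denominator is either all 532 randomized patients or the five of eight equal groups whose safety results are summarized (532 × 5/8 ≈ 332).
- 368 × 2/532 × 16/84 = 0.26
- 368 × 2/332 × 16/84 = 0.42
- 368 × 3/332 × 16/84 = 0.63

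That is about 0.3 to 0.6 across four arms, or roughly 0.1 per arm. Letting the gap vary from 13 to 19 days widens this to 0.26 × 13/16 = 0.21 and 0.63 × 19/16 = 0.75. These figures assume a constant rate and carry an IBS-C, on-treatment rate over to IBS-D patients off treatment.

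**6. Non-serious AEs recorded but outside every by-arm table.** The first day after last dose belongs to the Treatment Emergent Period. This leaves 14 − 1 = 13 days nominally, with a range of 11 − 1 = 10 to 17 − 1 = 16.

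**The case against.** The strongest reply is that the 30-day summary is supplementary. SAP 7.8.11.1 already has a table of treatment-emergent SAEs that lies wholly within the recording period. The extra summary may be meant only to keep known late SAEs and deaths from being dropped, and it does not itself say that new SAEs are solicited to day 30. This stands, and it limits the point to how the extra table is defined and read.

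A reader might infer that half of the SAE and death incidence goes unobserved. The documents do not support that. The uncovered share applies to post-dose days only, and the fatal outcome of an SAE already recorded can be ascertained under the 30-day follow-up rule. For the same reason, a plain cut of the table at the End-of-Study call could remove a death that the protocol does follow.

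A reader might also infer that post-treatment safety cannot be compared by arm at all. Post-treatment SAEs are summarized by arm in the very table discussed here; the gap concerns non-serious AEs, and those are listed. The 1-day limit is prespecified, and all safety analysis is descriptive, so what is missing is one count table.

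An assumed SAE rate of 1% to 3% would give 0.7 to 2.1 events in 16 days. That starts above what Protocol 3.3 implies, and none of the SAEs reported there occurred on the MD-7246 formulation.

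Finally, the length of the SAE reporting period may be set in the Safety Management Plan that the protocol's amendment summary mentions, which is not available here. What can be said is that the protocol and SAP do not define it.

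**Conclusion.** The point holds in a limited form. The SAE summary states a window that the described collection does not deliver for SAEs starting after the End-of-Study call: nominally 16 of 30 post-dose days, range 13 to 19. This assumes last dose at the Week 12 visit and no collection period set elsewhere. The expected number of affected events is below one across all arms, so the case rests on a table that can be misread, not on event volume.

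A larger gap for early terminators is possible but not established. Protocol 8.2.1.3 gives early termination only as an example, and Protocol 6.3 requires End-of-Treatment procedures without mentioning the later call. If recording did stop at termination, up to all 30 days would be uncovered.

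The second half also holds: about 13 of 14 post-treatment days of non-serious AEs have no by-arm summary, although the period has a declared safety purpose. Efficacy analyses and sample size are not affected. Both parts merit a change because the remedy is cheap.

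**What to change.** 1. In SAP 7.8.11.1, define the supplementary SAE and fatal-SAE summary by SAE onset, from first dose through the End-of-Study contact, or last contact for early terminators. Keep in the by-arm table any death up to day 30 that results from one of those SAEs. Show SAEs of later onset separately, labelled as passively ascertained. Record and justify the window in SAP Appendix 1. If another study document does set active SAE collection to 30 days, cite it in the SAP; the 30-day onset window could then stand.

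2. Add one descriptive table, by arm, system organ class and preferred term, of AEs with onset more than 1 day after last dose through the End-of-Study call.

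The cost is SAP wording and one extra descriptive table from data already collected. The drawback is a shorter stated onset window for SAEs.
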